A high-value CM intervention adapted from (Bisaga, Aharonovich et al. 2010) will be used to characterize participants on their ability to achieve initial MA abstinence during the second week of the lead-in period, a potential confounder of subsequent medication effects. Participants will be instructed at the first study visit that they will have the chance to earn gift cards for providing MA-free urine drug screens during the second week of the lead-in period. Participants will receive \$15 for the first MA-free urine provided during the second week, \$25 for the second MA-free urine provided, and \$40 for the third MA-free urine provided. Participants will be advised that achieving initial MA abstinence during the lead-in may be beneficial to their eventual treatment outcomes, but that failure to achieve abstinence will not affect their subsequent participation and those unable to abstain will be encouraged to complete the screening in order to avoid differential attrition. Participants will be stratified in secondary analyses by their ability to achieve MA abstinence with the CM intervention during the two-week lead-in period. All participants will receive \$25 in gift cards upon completion of the screening measures, regardless of urine drug screen results, to compensate participants for time spent completing screening measures. Participants who complete all baseline/eligibility assessments and meet all eligibility criteria will be randomized and begin study treatments and medication within 1 week of completion of screening measures

Eligibility Requirements: Participants randomized into the study must meet the following eligibility requirements:

Inclusion criteria:

- (1) 18 years of age or older;
- (2) meet DSM-IV-TR criteria for MA dependence (SCID verified);
- (3) a MA-positive urine drug screen at one or more visit during the two week lead-in period;
- (4) seeking treatment for MA problems;
- (5) willing and able to comply with study procedures;
- (6) provide written informed consent;
- (7) English speaking;
- (8) live within 35 miles of the clinical research site; and
- (9) if female of childbearing potential, not pregnant or lactating and willing to use a medically reliable method of birth control during the trial (e.g., birth control pills, Depo-Provera, and/or condoms with spermicide).

Exclusion criteria:

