- (1) a medical condition that, in the study physician's judgment, may interfere with safe study participation (e.g., active TB; unstable cardiac, renal, or liver disease; uncontrolled hypertension; unstable diabetes);
- (2) CD4 count < 50 cells/mm³ (suggestive of advanced HIV infection)
- (3) AST, ALT, or GGT > 3 times upper normal limit;
- (4) A corrected QT of > 450 msec in men or > 460 msec in women on at least two ECGs during the baseline period, or clinical risk factors for Torsades de Pointes (e.g., heart failure, hypokalemia, family history of Long QT Syndrome), or requiring ongoing treatment with

concomitant medication(s) with established risk of Torsades de Pointes (e.g. Amiodarone, Arsenic trioxide, Astemizole, Bepridil, Chloroquine, Chlorpromazine, Cisapride, Citalopram, Clarithromycin, Disopyramide, Dofetilide, Domperidone, Droperidol, Erythromycin, Flecainide, Halofantrine, Haloperidol, Ibutilide, Levomethadyl, Mesoridazine, Methadone, Moxifloxacin, Pentamidine, Pimozide, Probutol, Procainamide, Quinidine, Sotalol, Sparfloxacin, Terfenadine, Thioridazine, Vandetanib);

- (5) current ongoing treatment with psychotropic medications (e.g., antidepressants, antipsychotics, antiepileptics, sedative/hypnotics, narcotic analgesics);
- (6) a neurological disorder (e.g., organic brain disease, dementia) or a medical condition which would make study agent compliance difficult or which would compromise informed consent;
- (7) a major psychiatric disorder not due to substance abuse (e.g., schizophrenia, bipolar disorder) as assessed by the SCID;
- (8) attempted suicide in the past 3 years and/or serious suicidal intention or plan in the past year as assessed by the C-SSRS;
- (9) currently on prescription medication that is contraindicated for use with IBUD including alpha or beta agonists, theophylline, or other sympathomimetics;
- (10) current dependence on cocaine, opiates, alcohol, or benzodiazepines as defined by DSM-IV-TR;
- (11) alcohol dependence within the past year;
- (12) greater than one urine specimens during the lead-in with a riboflavin concentration of < 900 ng/ml as assessed via UV fluorescence;
- (13) a history of sensitivity to IBUD;
- (14) any other circumstances that, in the opinion of the investigators, would compromise participant safety; or
- (15) current participation in another clinical trial.

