Comprehensive feedback will be provided to subjects who are judged not suitable for the study for any psychiatric or medical reason. Participants who fail to complete all baseline data collection and procedures within two weeks will not be randomized into the trial. Subjects who are MA abstinent upon entry to the lead-in period are excluded as they are highly likely to remain abstinent regardless of treatment (Hillhouse, Marinelli-Casey et al. 2007).

Randomization Procedures: When participants are determined to be eligible and are cleared by the study physician for participation, they will be randomized to either IBUD 50 mg BID or placebo BID, stratified by baseline HIV serostatus (up to 70 HIV positive). In addition, within each strata an urn randomization procedure (Stout, Wirtz et al. 1994) will be used to provide multivariate balance across conditions along the following variables that may influence treatment outcomes: MA abstinent versus not abstinent as confirmed via urine drug screen during the second week of the lead-in period, (MA abstinence will be confirmed with at least two urine drug screens negative for presence of MA and no urine drug screen positive for MA, while all other urine drug screen results will be considered not abstinent), gender (biologic male versus female), ethnicity (Hispanic versus not Hispanic, marijuana dependence (dependent versus not as assessed by SCID), and baseline cognitive function (greater than 26 on the MoCA versus 25 or less). Participants will be considered to have entered the trial for the intention to treat analysis at the point of randomization. The randomization key will be maintained off-site in the Research office.

Outpatient Treatment Procedures: Participants will attend the outpatient research clinic twice weekly for urine drug screens, counseling, assessment of substance use and other standardized research measures (see below), and safety and medication adherence monitoring for 12 weeks of treatment. During this time repeat safety labs and a repeat EKG will be conducted at weeks 3 and 8. At week 13, a termination assessment will consist of a repeat physical, EKG, safety labs, and other behavioral assessments and cognitive testing, followed by a final brief health check 30 days later for post-medication safety monitoring.

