The initial MM session lasts 60 minutes and covers: (1) Review the results from his/her screening evaluation and address any medical concerns, (2) Use the results from the evaluation to support the diagnosis of MA dependence, provide basic information about the disorder (including prognosis), and advise abstinence, (3) Provide a rationale for and information about pharmacotherapy, (4) Provide a rationale for evaluating medication compliance at each session, (5) Use the patient's history of taking medication to establish an individualized plan that will ensure medication compliance, (6) Encourage participation in mutual-support groups (e.g., AA, SMART Recovery), and (7) Answer any questions or concerns about treatment. Follow-up visits last 20 minutes and cover: (1) A medical check on the participant's general functioning, (2) Review results of the participant's urine drug screens, (3) Review the participant's vital signs, (4) Ask about medication side effects and concurrent medications, (5) Perform a brief assessment of the participant's drug use and HIV risk behaviors, (6) Assess his/her medication compliance, and (7) Make recommendations for the participant to follow until the next visit.

To ensure integrity in the delivery of the counseling sessions, [name] will provide corrective feedback as needed to study clinicians, monitor adherence to the counseling manual through review of audiotaped sessions, and in weekly supervision meetings.

MA Urine Drug Screen Procedures: Participants will have a urine drug screen collected at each clinic visit that will be assessed for MA-metabolites using standard point of care immunoassay drug screen urine cups with a threshold of 300ng/mL. If a participant is unable to attend a clinic visit (e.g. out of town, holiday, etc.), subjects may provide drug screening samples using oral test kits.

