"Drop-out" Subject Tracking: Subjects who have not rescinded consent, but are no longer available/interested in attending twice-weekly visits ("drop-outs") will be followed using alternative methods. Every effort will be made for all subjects in the trial to attend a minimum of one clinic visit a week. However, attrition in Phase 2 trials tends to be high. In order to comprehend the reasons for dropping out of the clinical trial, we will arrange to meet the research subject weekly during the course of the medication phase of the trial at a mutually-agreeable location and/or taxi the participant to the clinic to collect a urine drug sample and complete data typically collected on a weekly basis.

Termination and Follow-Up Procedures: Once participants complete the 12-week medication period, they will be asked to return during week 13 for a repeat EKG, labs, and physical exam, and for follow-up assessment. On the final visit (approximately 30 days after completing study medications), participants will complete a brief health check with a study clinician. Every effort will be made to retain all participants through the entire trial. Our group has developed effective procedures for retaining individuals in controlled experimental drug trials (e.g., building strong relationships with study participants, telephone, texting, and letter procedures). Similar strategies will be implemented for this proposed study. However, we recognize that not all participants will complete the trial. Early termination criteria by the principal investigator are defined as two consecutive weeks (or four consecutive visits) of missed study activity or data collection visits. Participants who end the trial early, for whatever reason, will be asked to attend the 4-week follow-up visits.

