Structured Clinical Interview for DSM-IV (SCID) (Spitzer, Williams et al. 1995): Participants must meet DSM-IV criteria for methamphetamine dependence, as determined by the SCID during screening. A full SCID, as well as the Antisocial Personality Disorder (ASPD) subsection of the SCID-II will be completed by a study clinician (following training on the instrument) These results will be used to estimate the extent of co-morbid psychiatric diagnoses, and to verify that the participant does not have an active psychiatric disorder that precludes safe study participation.

Timeline Follow-Back method (TLFB) (Sobell, Sobell et al. 1986) will be used to determine days of use and quantities of use of cigarettes, alcohol, and other drugs over a 30-day period prior to screening. The same method anchored in the past 7 days will be used weekly during the second week of screening and during the medication and follow up phases.

Urinary Cotinine: Cigarette smoking status will be monitored biologically weekly via measurement of urinary cotinine.

Urine Drug Screening for benzodiazepines, marijuana, opiates, cocaine, and MA will be monitored using an onsite qualitative urine test device. Subjects will be warned that tampering with samples and taking OTCs that cross-react with the MA panel will be interpreted as positive for illicit substance use with consequences of being dropped from study participation. Urine drug screening will be completed at *each* study visit. If a participant is unable to attend a clinic visit (e.g. out of town, holiday, etc.), subjects may provide drug screening samples using oral test kits.

Urinary Riboflavin concentration will be measured on each urine specimen via fluorimetry using a Quantifluor Fluorometer (Promega Corp). Urinary riboflavin ≥ 900 ng/ml will be considered positive for active pill taking.

Vital Signs: Blood pressure, pulse, respiration rate, and temperature will be collected at each study visit.

Wender Utah Rating Scale (WURS) (Wender, 1995), administered during screening, retrospectively assesses ADHD-relevant childhood behaviors and symptoms in adults consisting of 25 items. Estimates of ADHD in the population of MA abusers are between 15%-35%.

Assessment of Neurocognitive Endophenotypes Implicated in MA Dependence

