During weeks 4 and 13, participants will repeat the following tasks: Montreal Cognitive Assessment; MATRICS CPT-II; HVLIT-R; BVMT-R; SST; TMT; DDT; WAIS-IV Letter Number Sequencing ; WAIS-IV Symbol Search, WAIS-IV Digit Symbol Coding; N-Back Task; DKEFS Color Word Interference and the Iowa Gambling Task.

Data Analysis: The primary objective of this study is to determine the efficacy of IBUD as a treatment for MA dependence and to provide FDA with sufficient data to advise whether IBUD should move forward for marketing as a MA dependence treatment. The primary outcome variable is the FDA-specified criterion of significant MA abstinence at the end of treatment defined as no self-reported MA use during the final two weeks of treatment (weeks 11/12) confirmed via urine drug screens (at least one of the two possible urine specimens each week is available during weeks 11 and 12 and all available urine specimens are MA-negative). The study is powered to detect a significant difference in the proportion of participants achieving this outcome in the IBUD versus placebo groups. Additional measures of clinically meaningful reductions in MA use during treatment will also be assessed in the event that IBUD produces effects on MA use that do not meet the abstinent at end of treatment threshold. In addition to MA use outcomes, treatment retention, an important clinical variable that is associated with long-term treatment outcomes in substance abuse treatment (Hser, Evans et al. 2004), with IBUD versus placebo will be compared. Effects of potential confounders on each of these outcomes will also be examined including: (1) medication non-adherence, (2) medication safety and tolerability (adverse event rates), and (3) ability to achieve initial MA abstinence with the CM intervention during the two week lead-in period.

A general univariate strategy will be used to test for differences between conditions at baseline and along all outcome variables using bivariate analyses (i.e., t-tests/ANOVA for continuous variables; χ^2 for dichotomous variables). A multivariate analysis will also be used when appropriate to control for co-variables known to influence MA dependence treatment outcomes including age, gender, baseline severity of MA dependence, HIV status, and ability to achieve initial abstinence during the CM lead-in.

Aim 1: To determine whether IBUD reduces MA use more than placebo among MA dependent participants.

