Power calculations: Power is calculated (Figure 5) for the primary study outcome: the proportion of participants achieving MA abstinence during the final two weeks of treatment (weeks 11 and 12) in the IBUD versus placebo group. This is the FDA-preferred outcome for stimulant pharmacotherapy trials and was used in a previous study that found an effect size of 0.5 for bupropion relative to placebo for MA dependence (Elkashef, Rawson et al. 2008). For a Fischer's exact test comparing the proportion achieving abstinence during final two weeks on IBUD versus placebo, with an effect size similar to that in the previous bupropion trial (0.5), a one-tailed test assuming IBUD will be superior to placebo, and an $\alpha = 0.05$, 55 participants are required in each group (total N = 110) to achieve 80% power. Our total sample size of 140 exceeds 80% power. Note that the use of the outcome variable abstinent during the final two weeks of treatment accounts for attrition as participants who fail to complete the trial fail to achieve urine drug screen confirmed abstinence during the final two weeks (i.e. missing considered non-abstinent). This is a conservative approach but appropriate as an effective medication would be expected to sustain patients in treatment for the allotted time in addition to facilitating abstinence as longer treatment retention and treatment completion are strong predictors of superior long-term outcomes and sustained abstinence (Ahmadi, Kampman et al. 2006, Hillhouse, Marinelli-Casey et al. 2007).

Figure 5: Power by total sample size (IBUD plus placebo) calculated with G*Power 3.1.0 (Faul, Erdfelder et al. 2007).

References:

- Ahmadi, J., K. Kampman and C. Dackis (2006). "Outcome predictors in cocaine dependence treatment trials." Am J Addict **15**(6): 434-439.
- Alhassoon, O. M., R. M. Dupont, B. C. Schweinsburg, M. J. Taylor, T. L. Patterson and I. Grant (2001). "Regional cerebral blood flow in cocaine- versus methamphetamine-dependent patients with a history of alcoholism." The international journal of neuropsychopharmacology / official scientific journal of the Collegium Internationale Neuropsychopharmacologicum **4**(2): 105-112.

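### Dropping randomised participants for a cross-reacting OTC product or tampering conflicts with the retention rules and loses primary-outcome data that could still be collected

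*Combined protocol and SAP*

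**What the plan says.** In the combined protocol and SAP, the Urine Drug Screening item of Study Measures and Assessments sets out a warning to participants. It covers sample tampering and OTC products: "taking OTCs that cross-react with the MA panel will be interpreted as positive for illicit substance use with consequences of being dropped from study participation". The MA result comes from "standard point of care immunoassay drug screen urine cups with a threshold of 300ng/mL" (MA Urine Drug Screen Procedures). No confirmatory assay is described.

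Other sections deal with leaving the study differently:

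- Termination and Follow-Up Procedures says "Every effort will be made to retain all participants through the entire trial". It defines the investigator's early-termination criterion as a run of missed visits.
- The drop-out tracking section provides weekly off-site urine collection. It describes this for people who are no longer available or interested, and does not mention people removed by staff.
- Study Medication Stopping Rules contains no OTC, tampering or positive-screen item. After medication is stopped, counseling continues up to week 12.

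The primary outcome (Data Analysis) requires that "at least one of the two possible urine specimens each week is available during weeks 11 and 12 and all available urine specimens are MA-negative", together with no self-reported use. Power calculations adds that "participants who fail to complete the trial fail to achieve urine drug screen confirmed abstinence during the final two weeks (i.e. missing considered non-abstinent").

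**The concern.** Read as written, the warning treats a participant who took a cross-reacting OTC product more severely than one who used MA. Both are scored positive for that specimen, but only the first is to be removed. After removal, the missing-equals-failure rule settles that participant's primary outcome without any further measurement.

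The outcome then reflects a staff decision about a specimen and not MA use at the end of treatment. The Aim 2 retention outcome and the secondary urine composites are affected in the same way. Each such case is a loss the trial could avoid, because the participant may be willing to go on giving samples.

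**Working it through.** **Step 1. Follow a participant through the rules.**

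| Event | Stays or dropped | Primary outcome |
|---|---|---|
| MA-positive screen in weeks 1–10, from MA use | Stays; no section removes for this alone | Can still succeed in weeks 11–12 |
| OTC-positive or tampered sample in weeks 1–10 | Dropped, if the warning is applied | No weeks 11–12 urine unless collected off-site, so failure |
| Either event in weeks 11–12 | Either | Failure already, because one positive is enough |

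The damage to the primary outcome is therefore confined to drops in weeks 1 to 10. Participants who end early are asked to attend the follow-up visits. Appendix II places these at weeks 13 to 16, after the outcome window.

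**Step 2. Other outcomes, for an illustrative drop at the end of week 4.**

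- Days retained (Aim 2 runs to the final clinic visit): 4 × 7 = 28 instead of 12 × 7 = 84.
- Treatment Effectiveness Score: at most 4 × 2 = 8 specimens instead of 12 × 2 = 24, so up to 16 are lost.
- The Joint Probability Index multiplies retention by abstinence, so it falls as well.

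**Step 3. The plan's own figure.** Power calculations states 55 per group for 80% power, from a one-tailed Fisher's exact test, alpha 0.05, effect size 0.5. Neither the scale of the effect nor a placebo rate is given.

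- As a standardised mean difference, n = 2(1.645 + 0.842)²/0.5² = 49.5, so 50 per group.
- As Cohen's h, exact Fisher enumeration needs 61 per group at a placebo rate of 5%, 59 at 10%, 58 at 15–25%, 57 at 30% and 56 at 35–40%.

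The stated 55 is close to these but cannot be reproduced exactly without the missing inputs. The point here does not depend on it.

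**Step 4. Sensitivity of power to drops.** Assumptions, none of them from the documents: h = 0.5; placebo abstinence p₁ of 0.10, 0.20 or 0.30; and a fraction f of would-be abstainers dropped before week 11 in both arms and never sampled again. From the documents: 70 per arm and a one-sided Fisher test at 0.05.

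The IBUD rate is p₂ = sin²(arcsin√p₁ + 0.25), giving 0.293, 0.428 and 0.544. Each rate becomes p(1 − f), so the risk difference shrinks by the factor (1 − f).

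| f | p₁ = 0.10 | p₁ = 0.20 | p₁ = 0.30 |
|---|---|---|---|
| 0 | 86.2% | 87.0% | 87.8% |
| 2% | 85.3% | 86.1% | 86.6% |
| 5% | 83.9% | 84.6% | 84.6% |
| 10% | 81.4% | 82.0% | 81.1% |
| 20% | 75.7% | 75.4% | 73.5% |

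In head count at p₁ = 0.20, expected abstainers are 70 × 0.20 = 14 on placebo and 70 × 0.4285 = 30 on IBUD. With f = 10%, about 1.4 + 3.0 = 4.4 participants are lost, and the difference falls from 0.2285 to 0.2285 × 0.90 = 0.206.

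**The case against.** The sentence is a deterrent warning. The plan gives no procedure for detecting OTC use or for deciding on removal, so the rule may seldom be applied. It can cause primary-outcome failures, but it does not force them. Study-level removal also exists elsewhere: Safety Procedures provides for discontinuing participants judged to be in danger. The medication stopping list concerns study medication, so the absence of an OTC item there proves little by itself. These points stand, and they limit the finding to a conflict that needs resolving and an avoidable loss of unknown frequency.

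A reader might go further in several ways that the documents do not support.

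- **That the rule contradicts intention to treat.** It does not. "Participants will be considered to have entered the trial for the intention to treat analysis at the point of randomization", and a dropped participant remains in the denominator as a failure, as the plan prescribes.
- **That an OTC positive in the lead-in would admit abstinent people through inclusion (3).** That criterion asks for "a MA-positive urine drug screen at one or more visit during the two week lead-in period". The argument uses the scoring half of the warning and ignores the removal half, under which such a person would be dropped.
- **That exclusion (9), the stopping criteria and the warning treat sympathomimetics inconsistently.** Exclusion (9) concerns people "currently on prescription medication that is contraindicated for use with IBUD including alpha or beta agonists, theophylline, or other sympathomimetics". The warning names no drug class, so linking the two needs outside knowledge.
- **That specimens with reported OTC use should be excluded in a sensitivity analysis.** Without a confirmatory assay, a participant who used MA could turn a failure into a success by reporting an OTC product. Scoring the specimen as positive is the safer rule.

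**Conclusion.** The conflict is real. Urine Drug Screening attaches removal to OTC cross-reaction and tampering. This does not fit the early-termination criterion and retention aim in Termination and Follow-Up Procedures, or the continued contact in Study Medication Stopping Rules. If applied in weeks 1 to 10, it turns a possible success into a failure and shortens days retained.

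Nothing in the documents suggests that this would differ by arm, so the expected effect is attenuation and lost power, not bias in favour of either arm. A chance imbalance in drops could move the observed difference, but that is not a systematic effect.

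The size cannot be established, because no OTC rate is given. On the assumptions in the working, losing 5 to 10% of would-be abstainers in both arms brings power from about 86–88% to about 81–85%, still above 80%. A loss of 20% would take it to about 74–76%. The change is worth making because the loss serves no analytic purpose and costs little to avoid.

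**What to change.** - In Urine Drug Screening, remove being dropped from the study as a consequence for randomised participants. Reconcile the sentence with Termination and Follow-Up Procedures and Study Medication Stopping Rules.
- State that a randomised participant with a suspect or cross-reacting specimen stays in urine and outcome collection to week 12, whatever is decided about study medication. Extend the weekly off-site collection to such participants where needed.
- State that the suspect specimen continues to be scored as MA-positive in the primary analysis.

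The cost is a few sentences of protocol text and, at most, off-site collection for a few more people. The downside is a slightly weaker deterrent against tampering.
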